3.2 Exclusion Criteria

- 1. Prior history of treatment with venetoclax. Prior ponatinib is allowed.
- 2. Active serious infection not controlled by oral or intravenous antibiotics (e.g. persistent fever or lack of improvement despite antimicrobial treatment).
- 3. History of acute pancreatitis within 1 year of study or history of chronic pancreatitis
- 4. Uncontrolled hypertriglyceridemia (triglycerides > 450mg/dL)
- Active secondary malignancy that in the investigator's opinion will shorten survival to less than 1 year.
- Active Grade III-V cardiac failure as defined by the New York Heart Association Criteria
- Clinically significant, uncontrolled, or active cardiovascular disease, specifically including, but not restricted to:
 - History of myocardial infarction (MI), stroke, revascularization, unstable angina or transient ischemic attack within the past 12 months
 - Left ventricular ejection fraction (LVEF) less than lower limit of normal per local institutional standards prior to enrollment
 - Diagnosed or suspected congenital long QT syndrome
 - Any history of clinically significant atrial or ventricular arrhythmias (such as uncontrolled artrial fibrillation, ventricular tachycardia, ventricular fibrillation, or Torsades de pointes) as determined by the treating physician
 - Prolonged QTc interval on pre-entry electrocardiogram (> 480 msec) unless corrected after electrolyte replacement
 - History of venous thromboembolism including deep venous thrombosis or pulmonary embolism within the past 3 months. Patients with a history of catheter associated upper extremity venous thromboembolism are not excluded.
 - Uncontrolled hypertension (diastolic blood pressure >100mmHg; systolic >150mmHg).
- 8. Patients currently taking drugs that are generally accepted to have a high risk of causing Torsades de Pointes (unless these can be changed to acceptable alternatives)
- 9. Received strong or moderate CYP3A inhibitors or inducers within 3 days of study entry
- 10. Consumed grapefruit, grapefruit products, Seville oranges, or star fruit within 3 days prior to starting venetoclax
- 11. Treatment with any investigational antileukemic agents or chemotherapy agents in the last 7 days before study entry, unless full recovery from side effects has occurred or patient has rapidly progressive disease judged to be life-threatening by the investigator. Prior recent treatment with corticosteroids and hydroxyurea is permitted.

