4. TREATMENT OF SUBJECTS

- 4.1. Variations in doses of the study agents or supportive care medications or dose schedules other than those suggested below are allowed if deemed to be in the best interest of patients. Such changes should be discussed with the principal investigator before they are instituted.
- 4.2. Treatment Overview The regimen consists of 4 cycles of induction/consolidation followed by up to 2 years of maintenance therapy for responding patients. For patients who have not received ponatinib within 2 weeks of the anticipated start date, the first cycle is 35 days, as single-agent ponatinib will be given for 7 consecutive days, after which venetoclax, ponatinib and corticosteroids will be given in combination. For patients who have received ponatinib within 2 weeks of the anticipated start date, the first cycle is 28 days, as the ponatinib single-agent lead-in will be omitted. For all patients, each consecutive cycle will be 28 days. Patients achieving remission will be referred to ASCT at the discretion of the treating physician, based on donor availability and suitability for ASCT. Patients will be removed from the study and will discontinue venetoclax at the time of ASCT. These patients will still be followed for survival analyses.
- **4.3** Cycle 1 (Induction) Patients who have not received ponatinib within 2 weeks of the anticipated start date will receive the following agents:
 - Ponatinib 45mg orally daily on days 1-35
 - Venetoclax orally in a daily dose escalation schema:

•							
		Day 8	Day 9	Day 10	Day 11	Day 12	Day 13-35
	Dose level -1 venetoclax	20 mg	50 mg	100 mg	200 mg	200 mg	200 mg
	Dose level 1 venetoclax (STARTING DOSE)	20 mg	50 mg	100 mg	200 mg	400 mg	400 mg
	Dose level 2 venetoclax	20 mg	50 mg	100 mg	200 mg	400 mg	800 mg

- Dexamethasone 40mg IV/PO on days 8-11
- CNS prophylaxis with methotrexate 12 mg intrathecally (IT) (6 mg via Ommaya reservoir) on day 9 (± 3 days) and cytarabine 100 mg IT on day 14 (± 3 days).
- For patients with CD20 expression (≥20% by flow cytometry), rituximab 375 mg/m² may be added at the discretion of the treating physician after the maximum dose of venetoclax has been reached. Rituximab will be given on day 14 (±3 days) and on day 21 (±3 days).

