Patients may receive ponatinib monotherapy on days 1-7 as an outpatient. Bone marrow will be performed on day 7 (±1 day) for correlative studies but must be prior to the initiation of venetoclax. Additional hydroxyurea or corticosteroids are allowed during the 7-day ponatinib lead-in after discussion with the PI.

Due to the potential for tumor lysis syndrome (see section 4.6), patients will be hospitalized the day prior to initiation of venetoclax and will remain hospitalized until 24 hours after the completion of the venetoclax dose escalation (day 12-14, depending on the dose level). Patients in both phase I and phase II cohorts will be hospitalized. Hospital stay may be

prolonged in patients with infections or other issues requiring inpatient stay. The remainder of the cycle can be administered as an outpatient. At the end of cycle 1, patients will have bone marrow aspirate/biopsy for response assessment.

For patients who have received ponatinib within 2 weeks of the anticipated start date, both venetoclax, ponatinib, and dexamethasone will be started on day 1 of the first cycle, and the 7-day lead-in of single-agent ponatinib will be omitted. Therefore, all days above will be moved forward 7 days, and the cycle will end on day 28.

4.3 Cycles 2-4 (Consolidation) – Patients will receive the following agents:

- Venetoclax orally at the maximum dose used in cycle 1, given daily on days 1-28
- Ponatinib orally daily on days 1-28. The dose of ponatinib will be adjusted according
 to the remission status as indicated by bone marrow assessment after cycle 1.
 - o Patients who have not received CR/CRi: 45mg daily
 - o Patients who have achieved CR/CRi but not CMR: 30mg daily
 - o Patients who have achieved CR/CRi with CMR: 15mg daily
- Dexamethasone 40mg orally daily on days 1-4
- CNS prophylaxis with methotrexate 12 mg IT (6 mg via Ommaya reservoir) on day 2 (± 3 days) and cytarabine 100 mg IT on day 7 (± 3 days).
- For patients with CD20 expression (≥20% by flow cytometry), rituximab 375 mg/m² may be added at the discretion of the treating physician. Up to 2 doses of rituximab may be given during each cycle.

All therapy can be administered in the outpatient setting. A total of 8 doses of IT chemotherapy are planned for cycles 1-4. A total of 8 doses of rituximab may be given for cycles 1-4. Any missed doses of rituximab or IT chemotherapy can be made up in subsequent cycles at the discretion of the treating physician.

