4.4. General Considerations

- Venetoclax must be administered with food
- Prevention of infection
 - o Prophylactic antibiotics may be given with each course until neutrophil recovery to $500/\mu L$ or greater
 - Suggestions include: Levaquin 500 mg orally daily (or other appropriate antibacterial agent); caspofungin or other appropriate antifungal agent; valacyclovir 500 mg orally daily or acyclovir 200 mg orally twice daily or other appropriate antiviral agent.
- Prevention and treatment of CNS disease
 - 8 prophylactic IT chemotherapy treatments are recommended. However, if the patient has had prior IT therapy, number of IT chemotherapy can be

- reduced if thought by the treating physician to be in the best interest of the patient after discussion with the PI.
- For patients with active CNS disease, consider methotrexate alternating with cytarabine twice weekly until CSF clear; then once weekly for 4 weeks, then back to prophylactic schedule. Consider XRT to the base of the skull, particularly with cranial nerve root involvement (cranial nerve palsies). Modifications to the regimen thought to be necessary for administration of XRT are allowed after discussion with the Pl.
- Venetoclax will provided by the Abbvie through the MDACC pharmacy. Ponatinib is indicated for the disease setting and will be charged to the patient/insurance.

4.5. Suggested Standard Dose Reductions/Modifications:

- Venetoclax

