 - o Moderate and strong CYP3A inducers and inhibitors are discouraged during venetoclax administraton. If a patient requires use of CYP3A inducers, use with caution. In many instances, such as antifungal prophylaxis with "azole" therapy in neutropenic patients, CYP3A inhibitors are required in ALL patients. Venetoclax should be administered at 50% dose reduction in the setting of moderate CYP3A inhibitors (i.e. isavuconazole, ciprofloxacin, diltiazem), and 75% dose reduction in the setting of strong CYP3A inhibitors (i.e. voriconazole), with the exception of posaconazole in which dose reduction should be approximately 83% (e.g. dose reduction to 70mg if patient would normally be taking 400mg). The venetoclax dose reduction should continue for the duration of co-administration. In the event the co-administered CYP3A inhibitor is discontinued, the assigned venetoclax dose should be resumed 2-3 days after discontinuation. During the venetoclax ramp-up, these agents must be held; however, they may be started or resumed 24 hours after the highest planned dose of venetoclax is given, along with the appropriate dose reduction of venetoclax as above.
 - o Non-hematological toxicity If grade 3 or 4 non-hematologic toxicity is attributable to venetoclax, dose interruption of venetoclax is required. Patients who experience drug-related grade 3 non-hematological toxicity may be given a subsequent course one dose level below the previous course, but the patient must have recovered to grade ≤1 before start of the next course. If a patient has drug-related grade 4 non-hematological toxicity, he/she may receive a subsequent course at one reduced dose level after resolution of toxicity to grade ≤1, only if approved by the PI based on the clinical significance of the toxicity and only if patient has had derived a benefit from the therapy. The dose of venetoclax can be decreased during a cycle, at the discretion of treating physician and PI, for chronic grade 2 non-hematological toxicity. Other dose modifications may be considered as clinically indicated with documentation and approval of the PI. The dose reduction guidelines for venetoclax are in the table below:

Current Venetoclax	Reduced Dose
Dose	
800mg	400mg
400mg	200mg
200mg	100mg
100mg	50mg
50mg	20mg

20mg	Hold venetoclax
------	-----------------

o Hematologic toxicity

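### In the ponatinib lead-in track, no rule sets an interval free of CYP3A inhibitors before the first venetoclax dose on day 8

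*Combined protocol and SAP*

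**What the plan says.** Section 3.2 has two neighbouring 3-day exclusions with different anchors. Item 9 excludes a patient who has "Received strong or moderate CYP3A inhibitors or inducers within 3 days of study entry". Item 10 excludes one who has "Consumed grapefruit, grapefruit products, Seville oranges, or star fruit within 3 days prior to starting venetoclax". Study entry is not defined.

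Cycle 1 has two tracks. Without recent ponatinib, "single-agent ponatinib will be given for 7 consecutive days, after which venetoclax, ponatinib and corticosteroids will be given in combination" (section 4.2), and the section 4.3 schedule puts the first venetoclax dose, 20 mg, on day 8. With recent ponatinib, "both venetoclax, ponatinib, and dexamethasone will be started on day 1 of the first cycle" (section 4.3).

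Section 4.5 discourages moderate and strong CYP3A agents while venetoclax is being given and requires them to be withheld during the ramp-up. They may start or restart 24 hours after the top dose, with venetoclax cut by 50% (moderate), 75% (strong) or about 83% (posaconazole; 70 mg in place of 400 mg). The cut lasts as long as the two drugs are given together. After the inhibitor stops, the assigned venetoclax dose returns 2-3 days later. Table 1 in section 5 lists these inhibitors as cautionary, with no interval.

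On infection prevention, section 4.4 states "Prophylactic antibiotics may be given with each course until neutrophil recovery", and its suggestions include "caspofungin or other appropriate antifungal agent".

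**The concern.** The 3-day window in exclusion 9 can serve as a washout before venetoclax only where venetoclax starts at about the time of entry. That is so in the recent-ponatinib track. In the lead-in track a week of ponatinib alone comes between, and a patient may begin an azole or another inhibitor in that week without breaking any rule.

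The stake is the opening of the ramp-up. It begins at 20 mg because of the tumor lysis risk, and residual inhibition could make the first dose, and possibly the second, act like a larger one. The plan treats such carry-over as relevant elsewhere: it waits 2-3 days before restoring the full dose, and it bars grapefruit for 3 days before venetoclax. In the lead-in track, grapefruit therefore has a pre-dose window and voriconazole has none.

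**Working it through.** **Step 1: days not covered.** Assume entry is day 1.
- Recent-ponatinib track: first venetoclax day 1, so 1 - 1 = 0 days between entry and first dose.
- Lead-in track: first venetoclax day 8, so 8 - 1 = 7 days (days 1-7).

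**Step 2: does another rule cover days 1-7?**
- Section 4.5, discouragement: applies while venetoclax is being given, so from day 8.
- Section 4.5, hold: applies during the ramp-up, so from day 8, with no lead time.
- Section 4.5, dose reduction: applies during joint administration. An inhibitor stopped on day 7 is never given together with venetoclax.
- Section 4.5, 2-3 day wait: governs the return to the assigned dose after joint administration, not a first dose.
- Section 5, Table 1: cautionary, no interval.
- Sections 6.1 and 6.2, medication checks: within 24 hours of the first dose (ponatinib in this track) and before each cycle. None is set for day 7 or 8.

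The inhibitor-free interval required before day 8 is therefore 0 days.

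**Step 3: which doses could be affected?** Apply the plan's own wait to a last inhibitor dose on day 7.
- 2-day wait: 7 + 2 = day 9, so day 8 falls inside the wait.
- 3-day wait: 7 + 3 = day 10, so days 8 and 9 fall inside it.

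**Step 4: ceiling on the effect.** The documents give no pharmacokinetic data. If the section 4.5 cuts are meant to offset exposure fully, the ceiling is nominal dose / (1 - reduction). For posaconazole the retained fraction is 70/400 = 0.175, a factor of 400/70 = 5.7.

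| Inhibitor | Factor | Day 8, 20 mg | Day 9, 50 mg (3-day carry-over only) |
|---|---|---|---|
| Moderate | 1/0.50 = 2 | 40 mg | 100 mg |
| Strong | 1/0.25 = 4 | 80 mg | 200 mg |
| Posaconazole | 1/0.175 = 5.7 | about 114 mg | about 286 mg |

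The planned doses are 50 mg on day 9 (50/20 = 2.5 times the first dose) and 100 mg on day 10 (100/20 = 5 times). On day 8 the moderate ceiling is below the next planned step, the strong ceiling lies between the next two, and the posaconazole ceiling is about 14% above the day-10 dose (114/100). These factors describe joint administration. Applied after the inhibitor has stopped, they are upper bounds, and the lower bound is no effect.

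**The case against.** The strongest reply is that the exposure is narrow and already guarded.

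- **Narrow.** Exclusion 9 means patients enter free of these agents, so the scenario needs an inhibitor started or restarted after entry and stopped just before day 8. Section 4.4 suggests caspofungin and Levaquin; it permits an azole but does not predict one. This stands.
- **Guarded.** Section 4.6 requires admission and IV hydration the day before venetoclax, a uric-acid reducer before the first dose, chemistries before and 6 hours after each new dose, investigator review before the next dose, and a stop for clinically significant TLS. Much of this acts before the first dose and addresses the harm in question. This stands too, but none of it lowers venetoclax exposure. The 48-hour dose-reduction rule is not counted here, because it appears under the heading for cycles 2 onward.
- **Only wording.** The 2-3 day interval is already in section 4.5, and section 4.1 allows schedules to vary. But as written the interval does not reach a first dose, and section 4.1 gives discretion rather than an instruction.

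A reader might infer more than the documents support:
- That inhibitors may be given alongside the ramp-up doses. The section 4.5 hold forbids it.
- That azole use on days 1-7 is routine, from the sentence "In many instances, such as antifungal prophylaxis with 'azole' therapy in neutropenic patients, CYP3A inhibitors are required in ALL patients". It belongs to the section 4.5 guidance on joint administration with venetoclax and says nothing about the lead-in.
- That DLT counts or the MTD would be distorted. Nothing in the documents gives the frequency or the size of effect needed to show that.
- That inducers pose the same risk. No harm from inducers is shown.

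**Conclusion.** The gap holds on the text: in the lead-in track a fully compliant patient can take a moderate or strong CYP3A inhibitor through day 7 and receive unreduced venetoclax on day 8. The absence of a rule is certain; the clinical consequence is not. Frequency is unknown, and the effect on the 20 mg dose ranges from none to a ceiling of 40, 80 or about 114 mg. Day 9 comes into question only if carry-over lasts the full 3 days and dosing was not stopped for TLS.

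The contrast between tracks assumes entry at or near day 1. If entry means an earlier registration, the gap in the lead-in track is wider and the recent-ponatinib track may lack a firm washout as well. Given the mitigation in section 4.6, this is a cheap improvement of modest priority.

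**What to change.** Keep exclusion 9 as it is: it still covers the days before ponatinib starts and can be checked at registration. Add one sentence to section 4.5: moderate and strong CYP3A inhibitors must be stopped at least 3 days before the first venetoclax dose (in the lead-in track, none on days 5-7, so the last dose is no later than day 4) and held through the ramp-up. For exceptions, section 4.1 already provides the route: "Such changes should be discussed with the principal investigator before they are instituted".

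Three days matches exclusions 9 and 10 and the upper end of the section 4.5 wait. Two days would meet the lower end, so the choice of three is partly a preference for consistency. Counting from the first venetoclax dose also removes the dependence on how study entry is defined, in both tracks.

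The cost is that some lead-in patients need a substitute for about 3 more days: caspofungin for an azole, Levaquin for ciprofloxacin, or an alternative to diltiazem. Eligibility, visits, sample size and analysis do not change.

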4. TREATMENT OF SUBJECTS

- 4.1. Variations in doses of the study agents or supportive care medications or dose schedules other than those suggested below are allowed if deemed to be in the best interest of patients. Such changes should be discussed with the principal investigator before they are instituted.
- 4.2. Treatment Overview The regimen consists of 4 cycles of induction/consolidation followed by up to 2 years of maintenance therapy for responding patients. For patients who have not received ponatinib within 2 weeks of the anticipated start date, the first cycle is 35 days, as single-agent ponatinib will be given for 7 consecutive days, after which venetoclax, ponatinib and corticosteroids will be given in combination. For patients who have received ponatinib within 2 weeks of the anticipated start date, the first cycle is 28 days, as the ponatinib single-agent lead-in will be omitted. For all patients, each consecutive cycle will be 28 days. Patients achieving remission will be referred to ASCT at the discretion of the treating physician, based on donor availability and suitability for ASCT. Patients will be removed from the study and will discontinue venetoclax at the time of ASCT. These patients will still be followed for survival analyses.
- **4.3** Cycle 1 (Induction) Patients who have not received ponatinib within 2 weeks of the anticipated start date will receive the following agents:
 - Ponatinib 45mg orally daily on days 1-35
 - Venetoclax orally in a daily dose escalation schema:

•							
		Day 8	Day 9	Day 10	Day 11	Day 12	Day 13-35
	Dose level -1 venetoclax	20 mg	50 mg	100 mg	200 mg	200 mg	200 mg
	Dose level 1 venetoclax (STARTING DOSE)	20 mg	50 mg	100 mg	200 mg	400 mg	400 mg
	Dose level 2 venetoclax	20 mg	50 mg	100 mg	200 mg	400 mg	800 mg

- Dexamethasone 40mg IV/PO on days 8-11
- CNS prophylaxis with methotrexate 12 mg intrathecally (IT) (6 mg via Ommaya reservoir) on day 9 (± 3 days) and cytarabine 100 mg IT on day 14 (± 3 days).
- For patients with CD20 expression (≥20% by flow cytometry), rituximab 375 mg/m² may be added at the discretion of the treating physician after the maximum dose of venetoclax has been reached. Rituximab will be given on day 14 (±3 days) and on day 21 (±3 days).

Patients may receive ponatinib monotherapy on days 1-7 as an outpatient. Bone marrow will be performed on day 7 (±1 day) for correlative studies but must be prior to the initiation of venetoclax. Additional hydroxyurea or corticosteroids are allowed during the 7-day ponatinib lead-in after discussion with the PI.

Due to the potential for tumor lysis syndrome (see section 4.6), patients will be hospitalized the day prior to initiation of venetoclax and will remain hospitalized until 24 hours after the completion of the venetoclax dose escalation (day 12-14, depending on the dose level). Patients in both phase I and phase II cohorts will be hospitalized. Hospital stay may be

prolonged in patients with infections or other issues requiring inpatient stay. The remainder of the cycle can be administered as an outpatient. At the end of cycle 1, patients will have bone marrow aspirate/biopsy for response assessment.

For patients who have received ponatinib within 2 weeks of the anticipated start date, both venetoclax, ponatinib, and dexamethasone will be started on day 1 of the first cycle, and the 7-day lead-in of single-agent ponatinib will be omitted. Therefore, all days above will be moved forward 7 days, and the cycle will end on day 28.

4.3 Cycles 2-4 (Consolidation) – Patients will receive the following agents:

- Venetoclax orally at the maximum dose used in cycle 1, given daily on days 1-28
- Ponatinib orally daily on days 1-28. The dose of ponatinib will be adjusted according
 to the remission status as indicated by bone marrow assessment after cycle 1.
 - o Patients who have not received CR/CRi: 45mg daily
 - o Patients who have achieved CR/CRi but not CMR: 30mg daily
 - o Patients who have achieved CR/CRi with CMR: 15mg daily
- Dexamethasone 40mg orally daily on days 1-4
- CNS prophylaxis with methotrexate 12 mg IT (6 mg via Ommaya reservoir) on day 2 (± 3 days) and cytarabine 100 mg IT on day 7 (± 3 days).
- For patients with CD20 expression (≥20% by flow cytometry), rituximab 375 mg/m² may be added at the discretion of the treating physician. Up to 2 doses of rituximab may be given during each cycle.

All therapy can be administered in the outpatient setting. A total of 8 doses of IT chemotherapy are planned for cycles 1-4. A total of 8 doses of rituximab may be given for cycles 1-4. Any missed doses of rituximab or IT chemotherapy can be made up in subsequent cycles at the discretion of the treating physician.

4.3 Cycles 5+ (Maintenance) – Patients will receive the following agents:

- Venetoclax at the maximum dose used in cycle 1, given daily on days 1-28
- Ponatinib orally daily on days 1-28. The dose of ponatinib will be adjusted according to the remission status as assessed by the last bone marrow assessment performed.
 - o Patients who have achieved CR/CRi but not CMR: 30mg daily
 - Patients who have achieved CR/CRi with CMR: 15mg daily
- Dexamethasone 40mg orally daily on days 1-4

All therapy can be administered in the outpatient setting. Up to 24 cycles of maintenance will be administered. The study will end 24 months after the last patient is enrolled.

